# Appendix 2 Physician's Global Assessment

# Global Assessment of Improvement

Target Lesions			
Lesion 1	Lesion 2		
☐ 100% improvement, no visible tumor	☐ 100% improvement, no visible tumor		
$\square$ 75% to <100% improvement	$\square$ 75% to <100% improvement		
$\square$ 50% to <75% improvement	$\square$ 50% to <75% improvement		
$\square$ 25% to <50% improvement	$\square$ 25% to <50% improvement		
☐ up to 25% improvement	☐ up to 25% improvement		
□ no change	□ no change		
□ worse	□ worse		

Nontarget Lesions				
Lesion 1	Lesion 2	Lesion 3		
☐ 100% improvement, no visible tumor	☐ 100% improvement, no visible tumor	☐ 100% improvement, no visible tumor		
$\Box$ 75% to <100% improvement	$\Box$ 75% to <100% improvement	$\square$ 75% to <100% improvement		
$\Box$ 50% to <75% improvement	$\Box$ 50% to <75% improvement	$\square$ 50% to <75% improvement		
$\square$ 25% to <50% improvement	$\square$ 25% to <50% improvement	☐ 25% to <50% improvement		
□ up to 25% improvement	☐ up to 25% improvement	☐ up to 25% improvement		
□ no change	☐ no change	☐ no change		
□ worse	□ worse	□ worse		

# Appendix 3 SCAR-Q

The SCAR-Q© is a rigorously developed patient-reported outcome (PRO) instrument that can be used to collect and compare evidence-based outcomes data from children and adults aged 8 years and older with a surgical, traumatic, or burns scar.

http://qportfolio.org/wp-content/uploads/2020/02/SCAR-Q-USERS-GUIDE-V1.pdf

# Appendix 4 FACE-Q

The FACE-Q© is a PRO measure that can be used to measure outcomes of aesthetic facial procedures and products from the patient's perspective. The FACE-Q© can be used to measure outcomes for any type of surgical or minimally invasive facial aesthetic treatment. This PRO instrument has been used to evaluate the safety and effectiveness of facial aesthetic treatments in numerous clinical trial settings and to inform patient care in clinical practice. The FACE-Q© is composed of a set of 39 independently functioning scales/checklists that measure 3 overarching domains: Facial Appearance, Health-Related Quality of Life, and Adverse Effects. These domains form the basis of the FACE-Q© conceptual framework (see link below). The FACE-Q© modular approach means that only the subset of scales most relevant to a specific research objective or clinical patient population need be administered.

 $\underline{http://qportfolio.org/wp\text{-}content/uploads/2020/02/FACE-Q-AESTHETICS\text{-}USER\text{-}GUIDE-}\underline{V1.pdf}$ 

Appendix 5 Scar Cosemesis and Rating Scale (SCAR)

Clinician Items	Scale Ratings	
Scar spread	0, None to near-invisible	
	1, Pencil-thin line	
	2, Mild spread, noticeable on close inspection	
	3, Moderate spread, obvious scarring	
	4, Severe spread	
Erythema	0, None	
	1, Light pink, some telangiectasias may be present	
	

Red, many telangiectasias may be present

	
	3, Deep red or purple	
Dyspigmentation (includes	0, Absent	
hyperpigmentation and hypopigmentation)	1, Present	
Track marks or suture marks	0, Absent	
	1, Present	
Hypertrophy/atrophy	0, None	
	1, Mild: palpable, barely visible hypertrophy or atrophy	
	2, Moderate: clearly visible hypertrophy or atrophy	
	3, Severe: marked hypertrophy or atrophy or keloid formation	
Overall impression	0, Desirable scar	
	1, Undesirable scar	
Patient items		
Have you been bothered by any	0, No	
itch from the scar in the past 24 h?	1, Yes	
Have you been bothered by any	O, No	
pain from the scar in the past 24 h?	1, Yes	
Total score range	0 (best possible scar) to 15 (worst possible scar)

## List of Abbreviations

AE	Adverse Event
ALP	Alkaline Phosphatase
ALT	Alanine Aminotransferase
AST	Aspartate Aminotransferase
ATC	Anatomical Therapeutic Chemical
ATCC	ATC Classification
AUC	Area under the plasma concentration-time curve
BCC	Basal Cell Carcinoma
BMI	Body Mass Index
BP	Blood Pressure
BUN	Blood Urea Nitrogen
CRA	Cutaneous Reaction Assessment
CS	Clinically Significant
CSR	Clinical Study Report
CV	Coefficient of Variation
DLT	Dose-limiting Toxicity
DMP	Data Management Plan
Dy	Day y, where y = 1, 2, 3
ECG	Electrocardiogram
EDC	Electronic Data Capture
EOS	End of Study
EOT	End of Treatment
FACE-Q	Patient-reported outcome measure for facial procedures
FA	Full Analysis
ICH	International Conference on Harmonization
LDH	Lactic Dehydrogenase
LLQ	Lower Limit of Quantitation
MCHC	Mean Corpuscular Hemoglobin Concentration
MCV	Mean Corpuscular Volume
MedDRA	Medical Dictionary for Regulatory Activities
MTD	Maximum Tolerated Dose

NCS	Not Clinically Significant
NTL	Non-target Lesion
PGA	Physician Global Assessment
PK	Pharmacokinetic
PN	Preferred Name
PP	Per-protocol
PT	Preferred Term
RBC	Red Blood Cell Count
RT	Reported Term
SCAR	Scar Cosmesis Assessment and Rating Questionnaire
SCAR-Q	Patient-reported outcome measure for scars (Note: not SCAR)
SAE	Serious Adverse Event
SAF	Safety
SAP	Statistical Analysis Plan
SD	Standard Deviation
SGOT	Serum Glutamic Oxaloacetic Transaminase
SGPT	Serum Glutamic Pyruvic Transaminase
SOC	System Organ Class
SRC	Safety Review Committee
TEAE	Treatment-emergent Adverse Event
TL	Target Lesion
TRAЕ	Treatment-related Adverse Event (same as related TEAE)
TRAЕ SI	TRAЕ of Special Interest
ULQ	Upper Limit of Quantitation
WBC	White Blood Cell Count
WxDy	Week x Day y, where x = 1, 2 and y = 1, 2, 3
WHO	World Health Organization
Wx	Week x, where x = 1, 2

## 1. Introduction

This Statistical Analysis Plan (SAP) describes the planned analysis and reporting for Verrica Pharmaceuticals Inc. protocol number VP-315-201 entitled “A Phase 2, Multicenter, Open-label, Proof-of-concept Study with Safety Run-in to Evaluate the Safety, Pharmacokinetics, and Efficacy of VP-315 in Adult Subjects with Basal Cell Carcinoma.”

This is an open-label, multicenter, proof-of-concept study with a safety run-in designed to assess the safety, tolerability, maximum tolerated dose (MTD), and objective antitumor efficacy of VP-315 when administered intratumorally to adults with biopsy-proven basal cell carcinoma (BCC).

Conveyed in this SAP are the planned analyses of the primary, secondary, and exploratory endpoints. This SAP and any modifications or changes must be finalized before the database is locked.

## 2. Objectives and Endpoints

The following objectives and endpoints will be considered.

Part 1	
Primary Objectives	Endpoints

 
To assess the safety, tolerability, and maximum tolerated dose (MTD) of ascending dose strengths of VP-315
 
	
 
Discontinuations due to adverse events (AEs); occurrence of dose-limiting toxicities (DLTs)
 
Cutaneous Reaction Assessment (CRA)
 

Exploratory Objectives 
 
To evaluate the objective antitumor efficacy of VP-315
 
	
 
Histological clearance of treated lesion(s) at excision
 
Clinical clearance of treated lesion(s) as determined by visual assessment (no tumor seen upon visible inspection) at excision
 
Estimate of remaining tumor volume (necrotic cells:tumor cells) at excision
 
Estimate of reduction in tumor volume (necrotic cells:tumor cells) at excision*
 
Abscopal effect as determined by
 

	
clinical and histological clearance of nontreated lesions at excision
 
 
• Physician Global Assessment (PGA)
 

Part 2 (Cohorts 1 and 2)	
Primary Objectives	Endpoints

 
• To determine the optimal regimen for dosing 8 mg of VP-315 based on safety and tolerability
 
	
 
• Treatment-related AEs; treatment-related serious adverse events (SAEs); discontinuations due to AEs; occurrence of TRAEs of special interest
 
• CRA
 

Secondary Objectives	Endpoints

 
• To evaluate the antitumor efficacy of VP- 315
 
	
 
• Clinical clearance of treated lesion at excision as determined by visual assessment (no residual tumor seen on visual inspection)
 
• Histological clearance of treated lesion(s) at excision
 
• Abscopal effect as determined by clinical and histological clearance of nontreated lesions at excision if nontreated lesions exist
 
• Estimate of remaining tumor volume (necrotic cells:tumor cells) at excision
 
• Estimate of reduction in tumor volume (necrotic cells:tumor cells) at excision*
 
• PGA
 

Exploratory Objectives	Endpoints

 
• To assess the immune response to VP-315 treatment in a subset of subjects by assessing the immune repertoire in blood and in tissue
 
	
 
• Multiplex immunohistochemical staining for T-cell subsets and immune activation markers in tumor tissue samples
 
• Analysis of T-cell clonality in blood and tumor tissue samples
 

 
• To assess subject satisfaction with the treatment
 
	
 
• SCAR-Q, FACE-Q
 

Part 2 (Cohorts 4 and 5)	
Primary Objectives	Endpoints

 
• To gain additional information on the
 
	
 
• Treatment-related AEs; treatment-
 

Verrica Pharmaceuticals Inc.  
Protocol: VP-315-201

Statistical Analysis Plan  
6-Sep-2024

safety, tolerability, and dosing regimen of VP-315 to support a pivotal study protocol design	related serious adverse events (SAEs); discontinuations due to AEs; occurrence of TRAEs of special interest 
 
● CRA
 

Secondary Objectives	Endpoints

 
● To confirm the antitumor efficacy of VP-315 using the optimal dosing regimen determined in Part 2
 
	
 
● Clinical clearance of treated lesion at excision as determined by visual assessment (no residual tumor seen on visual inspection)
 
● Histological clearance of treated lesion(s) at excision
 
● Abscopal effect as determined by clinical and histological clearance of nontreated lesions at excision if nontreated lesions exist
 
● Estimate of remaining tumor volume (necrotic cells:tumor cells) at excision
 
● Estimate of reduction in tumor volume (necrotic cells:tumor cells) at excision*
 
● PGA
 

 
● To characterize the pharmacokinetics (PK) of an 8 mg dose of VP-315 administered with the optimal dosing regimen determined in Part 2.
 
	
 
● Plasma VP-315 concentrations
 

Exploratory Objectives	Endpoints

 
● To assess subject and physician satisfaction with the treatment
 
● To assess the immune response to VP-315 treatment in a subset of subjects by assessing the immune repertoire in blood and in tissue
 
	
 
● SCAR-Q, FACE-Q
 
● Scar Cosmesis Assessment and Rating (SCAR) Scale
 
● Multiplex immunohistochemical staining for T-cell subset and immune activation markers in tumor tissue samples
 
● Analysis of T-cell clonality in blood and tumor tissue samples
 

\*Additional endpoint not included in protocol. Further details are included in section 14.

### 3. Study Design

This is a two-part study with sequential enrollment. All enrolled subjects will receive VP-315 intratumoral injections on an outpatient basis into up to two target lesions (TLs) and up to three non-target lesions (NTLs) will not be injected. Dosing will commence in a single TL. This study was expected to enroll approximately 80 subjects with a histologic diagnosis of BCC in at least one eligible TL (confirmed by punch or shave biopsy). Up to 15 study sites in the US will participate. The Schedule of Assessments can be found in Section 8.3 of the protocol.

#### 3.1. Part 1 (N = 10)

Subjects are to receive VP- 315 via once-daily dosing, with a starting total daily dose of 2 mg for the first cohort, escalating in 1 mg increments for subsequent cohorts after the current cohort has completed Week 1 dosing (the DLT observation period) and no DLT is observed. The planned dosing regimen is a split dose of VP-315 for all treatments. The  $\leq 500\mu\text{L}$  ( $\leq 8$  mg) dose is to be divided into 2 injections given at least 15 minutes and no more than 30 minutes apart, with 30% ( $\leq 150\mu\text{L}$ ) administered in the first injection and the remaining 70% ( $\leq 350\mu\text{L}$ ) with the second injection.

Subjects are to be treated until the lesion is necrosed or a DLT occurs, for a maximum of 2 weeks (W1D1, W1D2, W1D3 and W2D1, W2D2, W2D3 – up to 6 total doses increasing from the starting dose in 1 mg increments) and a maximum total daily dose of 8 mg. If the treated lesion necrosed and the subject has additional lesions, treatment of the next lesion may begin on D1 of the next week. A maximum of 2 TLs may be treated, and only 1 lesion may be treated at a time. DLT or visual confirmation of necrosis of all TLs will result in termination of VP-315 dosing.

#### 3.2. Part 2 (N = 82)

Subjects receive VP-315 via once-daily dosing, which is to be a total daily dose of 8 mg in up to 5 cohorts (i.e., there were no DLTs that occurred during Part 1, and the maximum dose of 8 mg was achieved).

#### 3.3. Cohort 1 (N = 6)

Subjects receive VP-315 via once-daily dosing of 8 mg with a loading dose of half the target dose of 8 mg (i.e., 4 mg) only on W1D1; all remaining doses are to be the full target dose without a loading dose. Subjects are to be treated until the lesion is necrosed, for a maximum of 2 weeks (W1D1, W1D2, W1D3 and W2D1, W2D2, W2D3 – up to 6 total doses). If the treated lesion necrosed and the subject has additional lesions,

treatment of the next lesion may begin on D1 of the next week. A maximum of 2 TLs may be treated, and only 1 lesion may be treated at a time.

### **3.4. Cohort 2 (N = 3)**

Subjects receive VP-315 via once-daily dosing of 8 mg on all treatment days (i.e., no loading dose on W1D1). Subjects are to be treated until the lesion is necrosed, for a maximum of 2 weeks (W1D1, W1D2, W1D3 and W2D1, W2D2, W2D3 – up to 6 total doses). If the treated lesion necrosed and the subject has additional lesions, treatment of the next lesion may begin on D1 of the next week. A maximum of 2 TLs may be treated, and only 1 lesion may be treated at a time.

### **3.5. Cohort 3 (N = 0)**

This cohort has been removed at the recommendation of the Safety Review Committee (SRC).

### **3.6. Cohort 4 (N = 36 [10 initial / 26 expansion] at two times weekly dosing)**

Subjects receive VP-315 via once-daily dosing of 8 mg, administered on 2 consecutive days in one week (W1D1, W1D2). The planned dosing regimen is a split dose of VP-315 for all treatments. The 500 $\mu$ L (8 mg) dose is to be divided into 2 injections given at least 15 minutes and no more than 30 minutes apart, with 30% (150  $\mu$ L) administered in the first injection and the remaining 70% (350  $\mu$ L) with the second injection. Treatment for a second TL may begin on D1 of the next week (W2D1, W2D2). Each individual TL is treated for the assigned 2 days only (regardless of necrosis status). Up to 2 TLs may be treated – up to 4 total doses. Subjects with only 1 TL who complete week one of treatment without complete necrosis receive no additional treatment.

### **3.7. Cohort 5 (N = 37 [10 initial / 27 expansion] at three times weekly dosing)**

Subjects receive VP-315 via once-daily dosing of 8 mg, administered on 3 consecutive days in one week (W1D1, W1D2, W1D3). The planned dosing regimen is a split dose of VP-315 for all treatments. The 500 $\mu$ L (8 mg) dose is to be divided into 2 injections given at least 15 minutes and no more than 30 minutes apart, with 30% (150  $\mu$ L) administered in the first injection and the remaining 70% (350  $\mu$ L) with the second injection. Treatment for a second TL may begin on D1 of the next week (W2D1, W2D2, W2D3). Each individual TL is treated for the assigned 3 days only (regardless of necrosis status). Up to 2 TLs may be treated – up to 6 total doses. Subjects with only 1 TL who complete week one of treatment without complete necrosis receive no additional treatment.

## 4. Dose-limiting Toxicity and Treatment-related Adverse Event of Special Interest

For Part 1 of the study, a dose-limiting toxicity (DLT) is defined as any of the following treatment-related adverse events (TRAEs) that occurs during the DLT period.

For Part 2 of the study, a treatment-related adverse event of special interest (TRAE SI) is defined as any TRAE that occurs during the treatment visit and meets the criteria below.

### 4.1. Treatment-related Adverse Events

TRAEs are treatment-emergent adverse events that are related to study treatment.

Adverse events (AEs) considered DLTs (Part 1) or TRAEs SI (Part 2) are defined as follows. AEs considered DLTs or TRAEs SI are captured in EDC.

- Hypotension meeting any of the following definitions:
  - > 20 mmHg decrease in systolic blood pressure (BP) with absolute systolic BP < 100 mmHg, or
  - > 20 mmHg decrease in systolic BP with clinical symptoms, or
  - absolute diastolic BP < 60 mmHg
- Significant elevation of serum tryptase concentration is defined as an increase of  $(1.2 \times \text{baseline value}) + 2$
- Any Grade 2 or higher AE occurring between start of dose administration and the end of the post-dose observation period on any given treatment day
- Any Grade 2 or higher AE considered by the investigator to be related to the investigational product
- Any Grade 2 or higher local reactogenic AE (injection site pain, erythema, induration)
- Any Grade 2 or higher systemic reactogenic AEs (fever, myalgia, headache)

## 5. Statistical Considerations

The statistical analyses will be reported using summary tables and data listings.

Numbering for the displays will be based on the recommended numbering convention provided by the International Conference on Harmonization (ICH).

## 5.1. Determination of Sample Size

No sample size calculations will be performed. However, the number of subjects enrolled in each study part should be adequate to meet the safety objectives and to provide preliminary evidence of efficacy.

## 5.2. Inferential and Descriptive Statistics

No formal inferential statistical analyses will be performed. Descriptive statistics for continuous variables will include number of subjects, mean, standard deviation, median, minimum, and maximum. Counts and percentages will be provided for categorical/ordinal variables. Unless specified in a display footnote, denominators for percentages will only consider the number of subjects being summarized or the number of non-missing responses being summarized, as appropriate. Conversion factors that may be used are as follows: 1 C = 33.8 F; 1 in = 2.54 cm; 1 kg = 2.2 lb; 1 month = 30.4375 days; 1 year = 365.25 days. The number of decimal places shown in displays will follow as closely as possible the below convention:

Statistic	Decimal Places *
n	0
Mean	1 more than Min, Max
Standard Deviation	2 more than Min, Max
Median	1 more than Min, Max
Min, Max	Same as most common in data
Percent	1

\* May be limited to less than stated as space provides

Tables will be summarized for scheduled visits unless stated otherwise in this SAP, and listings will be provided for data collected via the electronic data capture (EDC) system and from external vendor(s). If date of assessment, collection, measurement, and the like is not available, then date of visit will be used if available, where applicable. If there are multiple readings taken per visit, the most recent reading from that visit will be used in summaries, unless there are pre-dose and post-dose readings taken at the same visit, as mentioned elsewhere in this SAP.

The analyses described in this plan are considered *a priori*, in that they have been defined prior to database lock. Any analysis added after the database lock will be considered post hoc and exploratory. Post hoc analyses will be labeled as such on the displays.

Verrica Pharmaceuticals Inc.  
Protocol: VP-315-201

Statistical Analysis Plan  
6-Sep-2024

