## 8.4.2 Vital Signs Data

Height and weight will be obtained at Screening and EOS.

Vital signs (e.g., body temperature, BP, and heart rate [HR]) will be obtained at all visits after the subject has been in the supine position for at least 5-minutes. Vital signs will be measured at the final evaluation during the EOS visit before the subject is discharged from the study.

On VP-315 dosing days, blood pressure will be monitored serially (observing for hypotension that meets the definitions as described in Section 10.1): just prior to injection, at 1-, 3-, and 5-minutes after each injection, and then every 5-minutes until 2 hours after the last injection of the day using a manual or automated cuff system (Table 8-1). For subjects in Part 2 – Cohorts 4 and 5 expansion groups, monitoring of BP has been decreased to 1-hour post treatment (an additional hour may be continued at the discretion of the PI).

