### **5.7. Statistical Programming**

All analyses, tabulations, and validation programming will be performed using SAS version 9.4 or higher. Tables and listings will be presented in PDF format. SDTM datasets will be produced using Version 3.3 of the SDTM Implementation Guide. ADaM datasets will be produced using Version 1.1 of the ADaM Implementation Guide.

SDTM, ADaM, and tables will be validated by an independent programmer. The validation process will be used to confirm that statistically valid methods have been implemented and that all data manipulations and calculations are accurate. Checks will

be made to ensure accuracy, consistency with this SAP, consistency within tables, and consistency between tables and corresponding listings.

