Local reactogenicity is defined as the following events: Injection site pain, Erythema, Induration. For local reactogenicity, the PTs that will be used are as follows: Injection Site Pain, Injection Site Erythema, Injection Site Induration. Systemic reactogenicity is defined as the following events: Fever, Myalgia, Headache. For systemic reactogenicity, the PTs that will be used are as follows: Fever, Myalgia, Headache.

A separate listing will be provided for all AEs using the safety population, and the listing will include the following:

- Subject Experience any Adverse Events (Yes, No),
- Adverse Event,
- TEAE (Yes, No),
- DLT (Part 1) or TEAE SI (Part 2) (Yes, No),
- Start Date and End Date (or Ongoing),

- Severity (Mild, Moderate, Severe, Life-threatening, Death),
- Serious (Yes, No),
- Relatedness (Related, Not Related),
- Action Taken (No Action Taken, Dose Reduced, Dose Interrupted, Drug Withdrawn, Not Applicable),
- Outcome (Resolved/Recovered, Resolved/Recovered with Sequelae, Not Resolved/Not Recovered, Resolving/Recovering, Fatal, Unknown),
- Related to Screening (Yes, No), and
- Screening Assessment if Related to Screening.

Additionally, a separate listing will be provided for all SAEs using the safety population, and the listing will include the following:

- Serious Adverse Event,
- Start Date and End Date (or Ongoing) where End Date (or Ongoing) is taken from reported AEs,
- Report Version (Initial, Follow-up, Final),
- Reason for Reporting (Resulted in Death, Life-threatening, Required Prolonged Hospitalization, Persistent or Significant Disability, Congenital Anomaly/Birth Defect, Important Medical Event),
- Death Date,
- Hospitalization Date,
- Autopsy (Yes, No),
- Death Certificate (Yes, No),
- Date Event Became Serious, and
- Date Event Became Non-serious.

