### 9.3. Vital Signs Including Height and Weight

Summaries for vital signs will be provided using descriptive statistics and the safety population. Vital signs include the following parameters:

- Blood Pressure, Systolic (mmHg)
- Blood Pressure, Diastolic (mmHg)
- Height (cm)
- Weight (kg)
- BMI (kg/m^2)

- Heart Rate (beats/min)
- Respiratory Rate (breaths/min)
- Temperature (C)

Non-blood pressure vital signs (Height, Weight, BMI, Heart Rate, Respiratory Rate, Temperature) will be presented in one summary and blood pressure (Systolic, Diastolic) will be presented in other summaries (one each for systolic and diastolic).

Summaries will present scheduled visit and include baseline (Screening, Baseline, W1D1, W1D2, W1D3, W1 Safety Assessment, W2D1, W2D2, W2D3, W2 Safety Assessment, Limited Safety Assessment, EOT, EOS 1 Week Post-excision, EOS 2 Weeks Post-excision – not all vital signs are collected at all scheduled visits) within the parameters mentioned previously in this section of the SAP and include descriptive statistics for baseline and change from baseline for post-baseline visits, if possible.

Blood pressure is also to be measured and will be displayed by scheduled timepoint (Pre-injection, 1 Minute Post-injection, 3 Minutes Post-injection, and then 5 through 120 Minutes Post-injection in increments of 5 minutes) within injection (Injection 1, Injection 2 – not all timepoints are collected for all injections) within scheduled visit and include descriptive statistics for change from pre-injection for post-injection readings on that same visit, if possible.

A summary will also be provided for the number of events, and the number and percentage of subjects with at least one event, for each of the following parameters within injection visit (W1D1, W1D2, W1D3, W2D1, W2D2, W2D3):

- 20 mmHg decrease in systolic BP with absolute systolic BP < 100 mmHg
- 20 mmHg decrease in systolic BP with clinical symptoms
- Absolute diastolic BP < 60 mmHg

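### SAP 5.2 lists a single-point temperature equivalence as a conversion factor; any Fahrenheit body temperature converted with it would come out near 3 C

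*SAP*

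**What the plan says.** SAP 5.2, on inferential and descriptive statistics, has one sentence of unit conversions. It opens: "Conversion factors that may be used are as follows: 1 C = 33.8 F". It continues: "1 in = 2.54 cm; 1 kg = 2.2 lb; 1 month = 30.4375 days; 1 year = 365.25 days". The other four entries are all multiplicative.

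SAP 9.3 names temperature, in Celsius, among the vital signs. It says: "Summaries for vital signs will be provided using descriptive statistics and the safety population". The table is by scheduled visit, with change from baseline at post-baseline visits, and a listing gives each value, its unit and its change from baseline.

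Protocol 8.4.2 says: "Vital signs (e.g., body temperature, BP, and heart rate [HR]) will be obtained at all visits". It gives no unit for temperature, and neither do the vital-signs footnote to the Schedule of Assessments or any other part of the two documents.

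**The concern.** A factor converts by multiplication or division, which works only when the two scales share a zero. Celsius and Fahrenheit do not. The entry sits among true factors and carries that label, so the natural reading is that a Fahrenheit value is divided by 33.8. It is also the only temperature conversion the plan offers, so a programmer who follows the SAP has no correct rule to fall back on.

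At stake are the descriptive temperature table and the temperature entries in the vital-signs listing. Both levels and changes would be affected, because the divisor is wrong for each.

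**Working it through.** **Inputs.** Stated entry: 1 C = 33.8 F (SAP 5.2). Reporting unit: Celsius (SAP 9.3). Recording unit: not stated. The Fahrenheit readings below are illustrative.

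**Step 1: reproduce the plan's figure.** F = 1.8 × C + 32. At C = 1, F = 1.8 + 32 = 33.8. The entry is exact as a point equivalence.

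**Step 2: apply it as a factor.** Compare C = F / 33.8 with the correct C = (F - 32) / 1.8.

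| Reading (F) | F / 33.8 | (F - 32) / 1.8 |
|---|---|---|
| 97.0 | 2.87 | 36.11 |
| 98.6 | 2.92 | 37.00 |
| 100.4 | 2.97 | 38.00 |
| 104.0 | 3.08 | 40.00 |

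From 97.0 F to 104.0 F the factor spans 3.08 - 2.87 = 0.21, against a true span of 40.00 - 36.11 = 3.89 C.

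**Step 3: find where the two rules agree.** Set F / 33.8 = (F - 32) / 1.8. Then 1.8F = 33.8F - 1081.6, so 32F = 1081.6 and F = 33.8. They agree at that reading only, so no physiological Fahrenheit temperature converts correctly.

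**Step 4: changes.** The offset cancels in a difference, so a change in F should be divided by 1.8. A rise of 1.8 F is 1.8 / 1.8 = 1.0 C. The factor gives 1.8 / 33.8 = 0.05, too small by a ratio of 33.8 / 1.8 = 18.8.

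**Step 5: compare with the Protocol's own paired temperatures.** Protocol 7.2.2 pairs 2-8 °C with 36-46 °F and 20-25 °C with 68-77 °F. The offset formula gives 35.6-46.4 and 68-77, which agree after rounding. Multiplying by 33.8 gives 67.6-270.4 and 676-845. The Protocol's storage limits therefore follow the correct relation, not the SAP entry.

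**The case against.** The strongest reply is that nothing need go wrong. The equality is true, the list is permissive, and no passage tells anyone to divide by 33.8. No passage shows that any temperature was captured in Fahrenheit either; the US sites and the presence of the entry suggest it, but that is inference. SAP 5.7 requires independent validation that "statistically valid methods have been implemented and that all data manipulations and calculations are accurate", and a body temperature near 3 C would be conspicuous.

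Most of this stands, and it limits the consequence. It does not rescue the text. A permissive list that offers only an invalid rule still needs correcting. SAP 5.7 also has the validator check agreement with the SAP, so the written rule and the accuracy requirement pull in opposite directions.

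A reader might infer that the plan could not detect fever, and hence that DLT or TRAE SI counts are compromised. The documents do not support that. SAP 9.1 takes fever from adverse event terms: "Systemic reactogenicity is defined as the following events: Fever, Myalgia, Headache", with preferred terms named for each. SAP 4.1 says that DLTs and TRAE SIs are captured in EDC. SAP 9.3 plans threshold counts for blood pressure only and sets no temperature cut-off.

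**Conclusion.** The entry is wrong as a conversion rule and should be corrected; the severity is minor. The size of the error depends on two conditions that the documents do not establish: that some temperatures were recorded in Fahrenheit, and that they were converted literally by dividing by 33.8. If both hold, every such value is wrong by about 33 to 37 C over the range shown (36.11 - 2.87 = 33.24; 40.00 - 3.08 = 36.92), and changes shrink to about one nineteenth of their true size. If either fails, nothing is affected. It would therefore go too far to say that the temperature summary is wrong.

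The reach is confined to the temperature rows of the vital-signs summary and the matching listing entries. No efficacy endpoint or DLT, TRAE SI or adverse event count uses the conversion.

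A reader might extend the point to the rounded 2.2 lb per kg in the same sentence. That is ordinary rounding, worth about 0.21% (200 lb gives 90.9 against 90.7 kg). Doses are fixed in mg and the eligibility criteria set no weight or BMI limit, so it is not a defect.

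**What to change.** In SAP 5.2, replace the temperature entry with: C = (F - 32) / 1.8; a change in F is divided by 1.8. Confirm in EDC which unit was recorded for temperature, and whether it varied by site or record, so that only Fahrenheit values are converted. If all values were captured in Celsius, the entry can simply be deleted.

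The cost is one line of text and one data check. SAP Section 1 requires modifications to be final before database lock, so the change belongs before then. No design, sample size or other analysis is touched.
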